6.4 VISIT WINDOWING

Visit windowing will be considered only for efficacy and pharmacodynamic assessments.

The halfway point corresponding to the visits will be considered in relation to the date of first dose. Efficacy assessments are planned to be conducted at Week 2, Week 6, Week 12, Week 18, Week 24 and Week 28 visits. The following windowing rules will be taken into account to establish the visit corresponding to each efficacy and pharmacodynamic assessment:

- Week 2: any efficacy or pharmacodynamic assessment performed between 2 to 28 days after the first dose;
- Week 6: any efficacy or pharmacodynamic assessment performed between 29 days to 63 days after the first dose;
- Week 12: any efficacy or pharmacodynamic assessment performed between 64 days to 105 days after the first dose;
- Week 18: any efficacy or pharmacodynamic assessment performed between 106 days to 147 days after the first dose;
- Week 24: any efficacy or pharmacodynamic assessment performed between 148 days to 182 days after the first dose;
- Week 28: any efficacy or pharmacodynamic assessment performed between 183 days to 203 days after the first dose;

If two (or more) assessments are recorded within a visit window, the closer (closest) to the halfway point will be taken into account for the analyses. If two assessments within a visit window are the same number of days from the halfway point, the second one will be taken into account for the summaries assuming that it is more reliable than the first one.

No programmatic windowing of visits will be considered for safety data. Post-baseline data will be presented according to the visit at which it was collected on the eCRF or as described in this SAP.

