# 6.3.1 In case of Confirmed or Suspected Drug Induced Liver Injury

In case of any of the following events:

- Grade ≥ 2 severity liver-related AE, or
- Grade ≥ 3\_severity ALT or AST (i.e. ≥ 5x ULN), or
- Grade ≥ 2 severity total bilirubin (i.e. ≥ 1.5x ULN), or
- Grade  $\geq$  2 severity INR (i.e.  $\geq$  1.5x ULN)

The investigator will instruct the subject to interrupt IMP administration and to return to the study center within 2-3 days to perform a re-test and to undergo additional investigations (i.e. close monitoring as described in Appendix F) to assess for potential DILI. In case of confirmed or suspected DILI as assessed by the investigator, IMP administration must be permanently discontinued, in particular in the following cases:

• Re-test ALT and/or AST values ≥ 3 x baseline and greater than the ULN associated with new onset total bilirubin ≥ 2 x ULN or INR ≥ 1.5.

If subjects live in a remote area, they can be tested locally and the results communicated to the investigator site promptly.

In case of non-confirmed DILI, IMP administration will be resumed in accordance with the protocol and subject will remain under close monitoring as deemed necessary by the investigator.

Any confirmed or suspected DILI event will be closely monitored by the investigator and reported to Sponsor following the same procedure as for SAEs, as described in Section 9.5.

Withdrawals will be handled as described in Section 5.6.5.

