### **10.4.3.8** Other Statistical Analysis Considerations

All safety and efficacy data collected by visit will be summarized regardless of the visit window. For ECG, vital signs, laboratory results and efficacy assessments if there is more than one result

Protocol No.: GSN000300	Compound No.: GKT137831
Protocol Version No.: Final 4.0; Amendment 3	Sponsor: Genkyotex
Protocol Date: 24 July 2018	Author: Cmed Clinical Services

recorded for the same visit the non-missing value closest (if it is a planned, repeat or unscheduled assessment) to the planned day will be used in the summary tables and will be flagged into the corresponding listing. If there is more than one value closest to the planned day, the latest value will be used if the assessment was performed prior to the last dose of IMP.

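### SAP 6.4 keeps the result nearest an undefined halfway point, not the planned day as in Protocol 10.4.3.8; the main effect is at Week 6, the interim time point

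*SAP*

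**What the plan says.** SAP 6.4 assigns efficacy and pharmacodynamic results to windows counted from first dose. The interim time point has "Week 6: any efficacy or pharmacodynamic assessment performed between 29 days to 63 days after the first dose"; the window for the final primary endpoint is given as "Week 24: any efficacy or pharmacodynamic assessment performed between 148 days to 182 days after the first dose". If a window holds more than one result, "the closer (closest) to the halfway point will be taken into account for the analyses". The only explanation of the term is "The halfway point corresponding to the visits will be considered in relation to the date of first dose". On a tie, "the second one will be taken into account for the summaries", with no condition on dosing. SAP 6.6 brings unscheduled and repeat results into the windowed efficacy summaries.

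Protocol 10.4.3.8 has a different rule. With several results "recorded for the same visit the non-missing value closest (if it is a planned, repeat or unscheduled assessment) to the planned day will be used", and on a tie the latest is used only if it was taken before the last dose of IMP. SAP section 10 lists only the two-stage final analysis as a change to the planned analyses.

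Repeat samples are foreseen. After certain liver findings, Protocol 6.3.1 has the subject interrupt IMP and asks the subject "to return to the study center within 2-3 days to perform a re-test". Appendix F adds further liver tests two or three times a week.

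**The concern.** The two documents can select different records from the same data, and the SAP term has more than one possible meaning, so two programmers could also differ.

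The matter is most visible at Week 6. SAP section 9 makes Week 6 GGT the primary endpoint of the interim analysis and also analyses Week 6 ALP, ALT, AST and bilirubin. GGT, ALP, ALT, AST and total bilirubin also enter the repeated-measures models of SAP 8.7.2. If the reference day lies after the planned day, a repeat taken shortly after the visit tends to be preferred to the scheduled sample. After a liver finding, that repeat is taken with IMP interrupted, and it exists because the scheduled result was abnormal. Selection then depends on outcome, and it could differ by arm if the drug affects liver tests.

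**Working it through.** **1. Reproduce the window limits.** Take planned days as 7 x week after first dose: 14, 42, 84, 126, 168, 196. The points halfway between neighbouring visits are (14+42)/2 = 28, (42+84)/2 = 63, (84+126)/2 = 105, (126+168)/2 = 147 and (168+196)/2 = 182. These are the SAP's upper limits for Weeks 2 to 24. The windows are therefore built correctly, and they count days after first dose.

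**2. Compare window midpoints with planned days.** Midpoint = (lower + upper)/2.

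| Visit | Window | Midpoint | Planned | Shift | Shift if first dose = Day 1 |
|---|---|---|---|---|---|
| Week 2 | 2-28 | 15 | 14 | +1 | 0 |
| Week 6 | 29-63 | 46 | 42 | +4 | +3 |
| Week 12 | 64-105 | 84.5 | 84 | +0.5 | -0.5 |
| Week 18 | 106-147 | 126.5 | 126 | +0.5 | -0.5 |
| Week 24 | 148-182 | 165 | 168 | -3 | -4 |
| Week 28 | 183-203 | 193 | 196 | -3 | -4 |

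The last column is given because SAP 6.6 defines study day with first dose as Day 1, which adds 1 to every planned day.

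**3. On-time Week 6 visit.** Day 42 is |42-46| = 4 days from the reference. Repeats on Days 43 to 49 are at most 3 days away and win. Day 50 is also 4 days away and wins through the tie rule. For example, a re-test on Day 45 is 1 day from 46 and is kept. Under the planned-day rule the visit is kept (0 against 3 days).

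**4. Visits within the ±3-day tolerance (Protocol 7.3), with a re-test 2 or 3 days later.** This gives 7 x 2 = 14 combinations. The re-test wins under the SAP if its distance from the midpoint is no larger than the visit's.

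- Week 6, days after first dose: visits on Days 39 to 44 lose to both re-tests (12). A Day 45 visit ties with Day 47 and loses (1), but is kept against Day 48 (1 day against 2). Total 13 of 14.
- Week 6, first dose = Day 1: 11 of 14.
- Protocol rule: only visits 3 or 2 days early lose, 2 x 2 = 4 of 14. If the tie also goes to the re-test, a visit 1 day early loses at a 2-day lag, giving 5 of 14.
- Week 2: 7 of 14 (5 of 14 with first dose = Day 1), against the same 4 or 5 under a planned-day rule.
- Week 24: 0 of 14, because the midpoint lies before the planned day and a later re-test is always further from it.

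**5. Earlier samples at Week 24.** A Day 168 visit is 3 days from 165. An unscheduled sample on Days 163 to 167 is at most 2 days away and would displace it. Day 162 ties, and the later result, the visit, is kept.

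**The case against.** The strongest reply is that the protocol rule also lets a re-test win. It treats planned, repeat and unscheduled results alike, and it still gives 4 of 14. Its tie condition does not exclude a sample taken during a temporary interruption that is followed by further dosing. This stands: displacement by a re-test is made much more frequent at Week 6 by the halfway point, but it is not created by it.

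Other limits also stand:

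- A reader might infer that a 2-3 day re-test always replaces the Week 6 value. That is true for an on-time Day 42 visit, not for every visit within tolerance.
- A reader might put Week 2 on the same footing. The shift there is 1 day, or none with first dose as Day 1, and what remains comes from early visits and the tie rule.
- A reader might conclude that the interim primary endpoint is biased. Appendix F names ALT, AST, ALP, total bilirubin and INR, not GGT. GGT is in the study biochemistry panel (Protocol 8.2.1), so a re-test may include it, but this is not stated. Protocol 6.3.1 also allows local testing for remote subjects, and the documents do not say whether local results enter the efficacy data.
- The triggers are substantial, such as ALT or AST at 5 x ULN in subjects who entered at no more than 3 x ULN. Mandated does not mean frequent, and no frequency is given.

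It can also be said that the window midpoint is the natural reading, because the points halfway between visits are window edges and would make poor anchors. That is fair, but the midpoint still contradicts the protocol.

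**Conclusion.** The point holds as an undeclared contradiction between SAP 6.4 and Protocol 10.4.3.8, resting on an undefined term, with a material effect at Week 6. Under the midpoint reading the Week 6 reference is 4 days late (3 with first dose as Day 1), and a re-test 2-3 days after the visit is preferred in 13 of 14 combinations (11 of 14), against 4 of 14 under the protocol.

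These counts describe the rule. They are not probabilities. They weight all visit days equally and assume 2-3 days from scheduled sample to re-test, whereas the protocol counts from the instruction and gives no laboratory turnaround. At lags of 4 to 8 days an on-time Week 6 value is still displaced (up to 6 days with first dose as Day 1).

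The exposure is to ALT, AST, ALP and bilirubin, and to GGT only if it is re-tested. Neither the size nor the direction of any bias can be computed from the documents.

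A reader might infer that off-drug re-tests threaten the final primary endpoint. They do not by this route: a re-test after the Week 24 visit cannot displace it. Only an earlier unscheduled sample could, on Days 163-167 against a Day 168 visit. The interim analysis is also not meant to stop or amend the trial. The point should be corrected, but it does not undermine the final primary analysis.

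**What to change.** In SAP 6.4, replace the halfway point with the planned visit day for Weeks 2, 6, 12, 18, 24 and 28, and state the day count. In days after first dose, the count that reproduces the SAP's window limits, these are 14, 42, 84, 126, 168 and 196. Restore the protocol's tie condition, so that the later of two equidistant results is used only if it was taken before the last dose of IMP.

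This brings the SAP back to the protocol but leaves 4 or 5 of 14 combinations in which a re-test replaces an early visit. To close that gap, the sponsor may give the scheduled on-treatment sample priority over repeats in the same window. That goes beyond Protocol 10.4.3.8 and should be declared in SAP section 10 if adopted.

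The cost is two or three sentences and a small programming change before database lock, with no new data. If the interim analysis has already been run, its report should say which reference day was programmed.

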6.5 BASELINE

Baseline is defined as the last non-missing value/result where assessment date is less than or equal to the date of first dose, unless otherwise specified for individual assessments.

Baseline will be determined based on all assessments, including additional assessments.

Change from baseline is defined as the difference between the post-baseline assessment value and the baseline value.

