# 8.2 Laboratory Evaluations

# 8.2.1 Clinical Laboratory Evaluations

The following safety laboratory investigations will be conducted at time points indicated in "Schedule of Assessments" (Appendix A).

The following clinical safety laboratory tests will be performed at each visit:

- Hematology: hematocrit, hemoglobin, absolute and relative reticulocyte counts, red blood cell (RBC) count, white blood cell (WBC) count, differential WBC count, platelet count, absolute neutrophil count, mean cell volume and INR.
- Biochemistry: glucose, total protein, albumin, creatinine, urea, creatine kinase, total cholesterol, triglycerides, sodium, potassium, chloride, ALP, AST, ALT, conjugated and total bilirubin and GGT.
- TSH levels will be tested at each visit, except Visits 1 and 8. Free T4 will be also measured if TSH levels are ≥ 10 mIU/L.

Urinalysis (to be performed at Visits 1, 5, 7 and 8): quantitative test for pH and protein; qualitative tests for glucose, ketones, bilirubin, blood; microscopic examination of the sediment.

Viral serology will be performed at Screening (Visit 1): HIV antibodies (1 and 2), hepatitis B surface antigen and hepatitis C virus antibodies.

Determination of AMA will be performed at Screening (Visit 1): AMA titer, or if AMA is negative or in low titer (<1:80) PBC specific antibodies (anti-GP210 and/or anti-SP100 and/or antibodies against the major M2 components [PDC-E2, 2-oxo-glutaric acid dehydrogenase complex]).

Female subjects of child-bearing potential must have a negative serum pregnancy test documented at Screening (Visit 1). A negative urine pregnancy test must be done prior to study intervention at baseline/Day 1 (Visit 2) and all subsequent visits and the results must be available prior to dispensing of IMP.

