### **10.4.3.2 Primary Efficacy Analysis**

The mean of all assessments, including repeat assessments, prior to first dose will be considered as the baseline value for the analysis.

Due to the small sample size the primary analysis will be conducted using a stepwise approach. The percent change from baseline to Week 24 in serum GGT will be analyzed using an Analysis of Covariance (ANCOVA) with treatment and disease severity as fixed effects, and baseline GGT as a continuous covariate. If the normality assumption for the analysis is not met then the percent change from baseline in GGT at Week 24 will be analyzed non-parametrically through a stratified Wilcoxon Mann-Whitney (van Elteren) test. The normality assumption will be assessed through the examination of diagnostic residual plots. Further details and assumption checking will be provided in the SAP.

The difference between each dose of GKT137831 and placebo will be calculated, along with 95% and 97.5% confidence intervals of the difference (to account for Hochberg adjustment).

The primary analysis will be performed using the ITT population and a sensitivity analysis will be done using the PP population. If the Wilcoxon Mann-Whitney test is used, a subgroup analysis for disease severity will also be performed.

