#### Keys:

1. Day 1 (Visit 2) is also considered baseline of the 24-week double-blind treatment period (except for the determination of the primary endpoint where the mean of Screening (Visit 1) and Day 1 values will be defined as baseline).

2. Eligibility to enter the double-blind treatment period will be determined during Visits 1 and 2. Not every eligibility assessment needs to be repeated at Visit 2 i.e., confirmatory laboratory and diagnostic tests. Subjects with AEs at baseline may need to be withdrawn in accordance with the eligibility and withdrawal criteria.

3. At Screening (Visit 1), a serum pregnancy test will be performed. At all subsequent visits including baseline (Visit 2), urine pregnancy tests will be performed.

- 4. For the Baseline visit and all subsequent visits, subjects must remain fasted overnight from 10 pm and bring their morning dose to the clinic. Pre-dose samples will be collected and subjects will receive a breakfast meal. Subjects will then self-administer the morning dose up to 30 minutes after eating their meal. Post dose samples will be collected as described.
- 5. Post-dose, 12-lead ECG is to be performed around  $T_{max}$ , (i.e. 1 to 4 hours post dose).
- 6. A complete physical examination will be performed during the Screening visit (Visit 1) and at the follow-up (Visit 8). On all other visits a symptoms-directed physical examination will be performed.
- 7. Prior medication will be recorded at Screening only.
- 8. The IMP will be orally self-administered BID, once in the morning and once in the evening with meals or up to 30 minutes after eating a meal.

CONFIDENTIAL

Protocol No.: GSN000300	Compound No.: GKT137831
Protocol Version No.: Final 4.0; Amendment 3	Sponsor: Genkyotex
Protocol Date: 24 July 2018	Author: Cmed Clinical Services

9. PK sampling: one pre-dose PK sample will be collected. Subjects must bring their morning dose to the clinic) and two post-dose samples (first sample to be taken 1-2 hours after morning dose; second sample to be taken before subject leaves clinic but no earlier than 2 hours after the first post-dose sample) at Weeks 2 and 12 (Visits 3 and 5). A single post-dose sample (to be taken before subject leaves clinic at 3-4 hours after morning dose) at Week 18 (Visit 6).

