APRI	AST to Platelet Ratio Index		
AST	Aspartate Aminotransferase		
BID	Twice Daily		
CK-18	Cytokeratin-18		
CSR	Clinical Study Report		
DBP	Diastolic Blood Pressure		
ECG	Electrocardiogram		
eCRF	Electronic Case Report Form		
ELF	Enhanced Liver Fibrosis		
FDA	Food and Drug Administration		
FIB-4	Fibrosis-4		
GGT	Gamma Glutamyl Transferase		
hsCRP	High Sensitivity C-Reactive Protein		
ICH	International Conference on Harmonization		
lgM	Immunoglobulin M		
IMP	Investigational Medicinal Product		
IPF	Idiopathic Pulmonary Fibrosis		
ITT	Intent-To-Treat		
IWRS	Interactive Web-Based Randomization System		
LOCF	Last Observation Carried Forward		
MSAP	Modeling and Simulation Analysis Plan		
NADPH	Nicotinamide Adenine Dinucleotide Phosphate		
OCA	Obeticholic Acid		
OD	Once Daily		
РВС	Primary Biliary Cholangitis		

PD	Pharmacodynamic		
РК	Pharmacokinetic		
PP	Per Protocol		
QTcF	Corrected QT Interval (Fredericia's Formula)		
SAP	Statistical Analysis Plan		
SBP	Systolic Blood Pressure		
SMB	Safety Monitoring Board		
TEAE	Treatment-Emergent Adverse Event		
TSH	Thyroid-Stimulating Hormone		
UDCA	Ursodeoxycholic Acid		
ULN	Upper Limit Of Normal		
VAS	Visual Analog Scale		
WHO	World Health Organization		

3 Introduction

The purpose of this document is to describe the statistical methods, data derivations and data summaries to be employed in the analysis of study GSN000300 set up by Genkyotex in order to assess the efficacy and safety of oral GKT137831, a selective inhibitor of NOX 1 and 4 isoforms of the Nicotinamide Adenine Dinucleotide Phosphate (NADPH) oxidase family of enzymes, in patients with primary biliary cholangitis (PBC) receiving ursodeoxycholic acid (UDCA) and with persistently elevated alkaline phosphatase (ALP).

The preparation of this statistical analysis plan (SAP) has been based on International Conference on Harmonisation (ICH) E3 and E9 Guidelines and in reference to Protocol GSN000300 Version 4.0 (Amendment 3, 24 July 2018) and CRF Version 6.4 (12 February 2019).

4 Study Objectives

PRIMARY OBJECTIVE

The primary objective of the study is defined as follows:

• To evaluate the efficacy of oral GKT137831 in comparison with placebo, in subjects with PBC receiving UDCA and with persistently elevated serum ALP.

SECONDARY OBJECTIVES

The secondary objectives of the study are defined as follows:

- To evaluate the safety of oral GKT137831 in comparison with placebo, in subjects with PBC receiving UDCA and with persistently elevated serum ALP.

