6.6 REPORTING GUIDELINES

The following guidelines will be followed:

- Page Orientation: Landscape.
- **Post-text tables and listings**: will be generated in .lst and converted to rtf.
- **Post-text figures**: will be generated directly in .rtf.
- **Font**: Courier New font with minimum of 9 points font size.
- Margins: Left: 3.8 cm, Right: 2 cm, Top: 3 cm, Bottom 2 cm on A4 paper.
- Columns headers will be left aligned.
- **Treatment labels** will be the following and displayed in the following order, unless otherwise stated:
 - o GKT831 400mg OD
 - o GKT831 400mg BID
 - o Placebo
 - o **Total**
- Visit labels: the visit labels displayed in Table 1 will be used as required.

Table 1: Visit Labels

Study Stage	CRF Visit	Tables, Figures and Listings Label
Screening	Visit 1 (Screening): Day -28 to -7	SCR
	Visit 2 (Baseline): Day 1	BAS
	Visit 3: Week 2 +/- 3 days	TRT W2
Treatment phase	Visit 4: Week 6 +/- 3 days	TRT W6
Treatment phase	Visit 5: Week 12 +/- 3 days	TRT W12
	Visit 6: Week 18 +/- 3 days	TRT W18
	Visit 7: Week 24 +/- 3 days	TRT W24
Follow-up phase	Visit 8: Week 28 +/- 3 days	FU W28

- Unscheduled visit / repeat assessments: Data obtained at unscheduled or repeat assessments will be taken into account in baseline determination and efficacy summaries based on windowed visits. All other data from unscheduled or repeat assessment will not be included in summaries but only be presented in data listings, unless otherwise specified.
- **N:** The number of subjects in the specified population.
- **Treatment presentation:** The summaries will be presented by allocated or actual treatment group (see more details in Section 7) and overall for disposition, demographics and baseline characteristics, protocol deviations, concomitant medications, study drug exposure and compliance.
- **Continuous data** will be summarized using number of subjects (n), mean, standard deviation (SD), median, minimum value, maximum value and number of missing data (if there are any).
- **Categorical data** will be summarized using n and percentage based on number of nonmissing data.
 - All categories will be presented, even if no subjects are counted in a particular category.
 - In case 1 or more subjects have missing data for the summary, the number of missing data will be presented as a separate category, labelled accordingly as 'Missing', if not otherwise stated.
 - Counts of zero in any category will be presented without percentage.

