8.7 EFFICACY DATA ENDPOINTS AND ANALYSES

8.7.1 Primary Efficacy Endpoint and Analyses

The clinical response to GKT137831 is defined as the percent change from baseline to Week 24 visit in serum GGT (primary efficacy endpoint).

Absolute serum GGT values as well as absolute change and percent change from baseline to Week 24 visit in serum GGT values will be provided at baseline and Week 24 visit for each allocated treatment group using summary statistics.

Due to the small sample size, the primary analysis will be conducted using a stepwise approach. The percent change from baseline to Week 24 visit in serum GGT will be analyzed using an Analysis of Covariance (ANCOVA) with the allocated treatment and disease severity at baseline as fixed effects, and the serum GGT baseline value as a continuous covariate.

The least square means estimate of the difference between each dose of GKT137831 and placebo alongside the 95% confidence interval will be calculated. Given two doses of GKT137831 are tested versus placebo, the 97.5% confidence interval of the least square mean of the difference between each dose of GKT137831 and placebo will also be calculated to account for the multiple testing using Hochberg adjustment.

If the normality assumption for the primary analysis is not met then the percent change from baseline in serum GGT at Week 24 will be analyzed non-parametrically through a stratified Wilcoxon Mann-Whitney (van Elteren) test. The normality assumption will be assessed through the examination of diagnostic residual plots.

The primary analysis will be performed using the ITT population and a sensitivity analysis will be done using the PP population. If the Wilcoxon Mann-Whitney test is used, a subgroup analysis for disease severity will also be performed.

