The interim analysis will be conducted by the unblinded SMB statistician, who has no involvement with the study conduct. The interim analysis outputs will be communicated to the Sponsor's Chief Medical Officer.

The interim analysis described above does not include assessments of safety data. The safety data will be reviewed periodically and separately as described in the study SMB charter.

10 Changes to Planned Analyses

The final analysis will be performed according to a 2-stage process detailed in Section 6.1.

11 Document History

Date	Version	Modified by	Brief details of changes made to template
150CT2018	1.0	[name]	Initial final version
15MAR2019	2.0	[name]	Updated final version The main changes are the following: 1. Addition of Section 6.1 to clarify the timing of the final analysis. 2. Addition of Appendix 1 to provide the list of Top Line tables.

12 References

[1] New Drug Application (NDA) 207999 submitted by Intercept Pharmaceuticals, Inc. for obeticholic acid (OCA) proposed for the treatment of Primary Biliary Cirrhosis (PBC), Gastrointestinal Drug Advisory Committee (GIDAC) Meeting, April 7th, 2016.

[2] Hirschfield GM et al. Efficacy of Obeticholic Acid in Patients With Primary Biliary Cirrhosis and Inadequate Response to Ursodeoxycholic Acid. Gastroenterology 2015; 148: 751-761.

[3] CTCAE v4.03:

http://evs.nci.nih.gov/ftp1/CTCAE/CTCAE_4.03_2010-06-14_QuickReference_5x7.pdf

13 Appendix 1: List of Top Line tables

Table order	Table number	Table title
1	14.1-1	Subject Disposition (Randomized Population)
2	14.1-3	Summary of Demographic and Baseline Characteristics (ITT Population)
3	14.1-5.1	Disease Characteristics (ITT Population)
4	14.2-1.1.1	Summary of Absolute and Percent Change from Baseline to Week 24 Visit in Serum GGT (ITT Population)
5	14.2-1.1.2	Analysis of Percent Change from Baseline to Week 24 Visit in Serum GGT (ITT Population)
6	14.2-1.3.1.1	Summary of Percent Change from Baseline to Week 24 Visit in Serum GGT by Subgroup of Baseline GGT values (ITT Population)
7	14.2-1.3.1.2	Analysis of Percent Change from Baseline to Week 24 Visit in Serum GGT by Subgroup of Baseline GGT values (ITT Population)
8	14.2-2.1.1	Summary of Absolute and Percent Change from Baseline to each Post- Baseline Visit in Serum GGT (ITT Population)
9	14.2-2.1.2	Analysis of Percent Changes from Baseline in Serum GGT across all Post Baseline Visits [a] Model Estimates (ITT Population)

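### The protocol averages pre-dose GGT values for the primary-endpoint baseline; the SAP takes the single last value, makes no exception for GGT and declares no change.

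*SAP*

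**What the plan says.** **Protocol.** Section 10.4.3.2, on the primary analysis: "The mean of all assessments, including repeat assessments, prior to first dose will be considered as the baseline value for the analysis". Appendix A Key 1 takes Day 1 as baseline in general, "except for the determination of the primary endpoint where the mean of Screening (Visit 1) and Day 1 values will be defined as baseline". Two pre-dose values are planned for every subject: Section 8.2.1 says "The following clinical safety laboratory tests will be performed at each visit", and GGT is in the biochemistry list.

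**SAP.** Section 6.5: "Baseline is defined as the last non-missing value/result where assessment date is less than or equal to the date of first dose". It leaves room for a different rule for an individual assessment. Section 8.7.1 defines the primary endpoint and model but refers only to "the serum GGT baseline value as a continuous covariate", with no definition of its own. Section 6.6 adds that "Data obtained at unscheduled or repeat assessments will be taken into account in baseline determination". That says which values are eligible, not that they are averaged.

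The SAP says it was prepared "in reference to Protocol GSN000300 Version 4.0 (Amendment 3, 24 July 2018", the version that contains the mean rule. Section 10, Changes to Planned Analyses, has one entry: "The final analysis will be performed according to a 2-stage process detailed in" Section 6.1.

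**The concern.** Baseline GGT enters the primary analysis twice, as the denominator of the percent change and as the ANCOVA covariate. A programmer following the SAP will compute a different endpoint and a different covariate from those in the protocol. The primary result is therefore not uniquely pre-specified across the two governing documents, and a reader of the study report could not tell whether the rule used was chosen before or after the data were seen. Key 1 singles out the primary endpoint by name, so the mean looks like a deliberate design choice. The documents do not show whether the SAP dropped it on purpose or failed to carry it over.

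**Working it through.** **1. The rules side by side**

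| Place | GGT baseline for the primary endpoint | Repeats |
|---|---|---|
| Protocol 10.4.3.2 | mean of all pre-dose values | included |
| Protocol Appendix A, Key 1 | mean of Screening and Day 1 | not mentioned |
| SAP 6.5 (no exception in 8.7.1) | single last value on or before the date of first dose | eligible, not averaged |

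The two protocol rules coincide when there are no repeats. The SAP rule differs from both whenever Screening and Day 1 differ.

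**2. The plan's own figure.** Inputs (Protocol 10.2, SAP 5.4): 34 per arm, difference 28, SD 30 active and 40 placebo, two-sided alpha 0.023475, Wilcoxon Mann-Whitney test.
- Common SD = sqrt((30² + 40²)/2) = 35.36.
- The normal formula gives 31 per arm; dividing by the Wilcoxon efficiency, 31/0.955, gives 33.
- Noncentral-t power at an effective n of 34 × 0.955 = 32.47 is 80.5%. Simulating the Wilcoxon test gives 79.8%.

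The stated 80% reproduces. The text does not say which baseline the SDs refer to, so both readings are carried below.

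**3. One subject (assumed values).** Screening 300, Day 1 240, Week 24 200 IU/L.
- Mean baseline: 200/270 − 1 = −25.9%.
- Last value: 200/240 − 1 = −16.7%.
- With Screening and Day 1 exchanged, the mean still gives −25.9% and the last value gives 200/300 − 1 = −33.3%.

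**4. Precision.** Assume a within-subject CV (in %) and similar, independent errors at Screening and Day 1. One baseline value contributes about CV² to the placebo variance of percent change; a mean of two contributes CV²/2. The last value therefore adds about 0.5 × CV², against a planned 40² = 1,600. In the active arm the term is scaled by (1 − 0.28)² = 0.5184.

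Example at CV 10%, if the SDs refer to a single value:
- Last value: SE = sqrt((1,600 + 900)/34) = 8.57; 28/8.57 − 2.266 = 1.00; power 84.1%.
- Mean: SE = sqrt((1,550 + 874.1)/34) = 8.44; 28/8.44 − 2.266 = 1.05; power 85.3%.
- Gain: 1.2 points.

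The simulation used 10,000 three-arm trials per scenario, 34 per arm, and the planned ANCOVA tested pairwise at 0.023475. It assumed log-normal GGT (median 5 × ULN, log-SD 0.7) and Screening at or above 1.5 × ULN, with percent-change SDs calibrated to 40 and 30 under each reading.

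| CV | Added placebo variance | Gain from mean, normal approx. | Gain, simulated | SE last v mean (SDs for single value) | SE last v mean (SDs for mean) |
|---|---|---|---|---|---|
| 5% | 12.5 | 0.3 | 0.2–0.3 | 8.68 v 8.63 | 8.72 v 8.67 |
| 10% | 50 | 1.2 | 1.2 | 8.70 v 8.50 | 8.88 v 8.68 |
| 15% | 112.5 | 2.7 | 2.2–2.6 | 8.59 v 8.16 | 9.21 v 8.82 |
| 20% | 200 | 4.7–4.8 | 3.7–4.8 | 8.58 v 7.79 | 9.43 v 8.64 |
| 25% | 312.5 | 7.2–7.5 | 5.1–6.8 | 8.40 v 7.18 | 9.73 v 8.59 |

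Gains are in percentage points of power; the Monte Carlo SE of each simulated gain is 0.1 to 0.3. A median of 3 × ULN instead of 5 at CV 20% gives a gain of 3.8 against 3.7 points.

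**5. Effect on the result.** Under a true 28-point effect, the two rules reach different significance decisions in 2% to 10% of trials across these CVs, and their estimates differ with an SD of 0.8 to 4.1 percentage points. With no true effect, their rejection rates differ by at most 0.3 points (CV 5, 15 and 25%).

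**6. When the mean stops helping.** Setting (CVs² + CVd²)/4 = CVd², with s for Screening and d for Day 1, gives CVs = √3 × CVd = 1.73 × CVd. With Screening at 1.5, 1.73 and 2 times the Day 1 CV, the simulated gain of the mean is +0.2, −0.3 and −1.0 points at a Day 1 CV of 10%, and +1.9, +0.4 and −1.0 at 20%.

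**The case against.** The best defence is that the SAP, read alone, is unambiguous. It is final, and Protocol 10.4.3.2 leaves further details to it. The consequences may also be small: the same rule applies in every arm, so there is no bias; at a CV of 10% or less the power gap is at most 1.2 points; and with the last value, simulated ANCOVA power stays at about 81% to 91%, above the planned 80% in every scenario (the van Elteren fallback was not covered). If the planning SDs refer to a single value, nothing is lost against the plan and only a gain is forgone. The last value may even be the better choice, because Screening is used for eligibility and the overnight-fast rule in Key 4 starts only at the Baseline visit. Finally, Key 1 limits the mean to the primary endpoint, so the SAP's single rule avoids having two GGT baselines in one report.

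The points about size stand. So does the last one in part: the primary ANCOVA with LOCF and the repeated-measures model in SAP 8.7.2 will give two Week 24 estimates whatever the baseline, so that duplication is no argument for either rule. None of this removes the conflict. Leaving details to the SAP does not authorise replacing a rule the protocol states outright, and SAP Section 10 is where such a replacement belongs. SAP Section 5.2 twice cites Protocol Version 3.0, so carry-over from older text is possible, but that would explain the discrepancy without resolving it.

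**Conclusion.** The concern holds and should be corrected before unblinding. The protocol and SAP prescribe different baselines for the sole primary endpoint, and the difference is neither excepted nor declared. This needs no assumption about variability. It is a failure of pre-specification, not a bias between arms and not a shortfall below 80% power. The loss of precision with the last value is probable but not certain: from negligible at a CV of 5% to about 5 to 7 power points at 25%, given an assumed CV and Screening values about as reliable as Day 1 values. It reverses if the Screening CV exceeds about 1.73 times the Day 1 CV.

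**What to change.** Add to SAP Section 8.7.1, before unblinding:

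> For the primary endpoint, baseline serum GGT is the arithmetic mean of all values obtained before first dose (Screening, Day 1 and any repeats). It is used for both the percent change and the ANCOVA covariate. A sensitivity analysis uses the last value before first dose.

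If the sponsor prefers the last value, Section 10 should declare and justify the change, with the mean as the sensitivity analysis. In either case:
- state which baseline the repeated-measures GGT analysis (Section 8.7.2) and the Week 6 interim GGT analysis (Section 9) use, since Key 1 limits the mean to the primary endpoint;
- align Protocol 10.4.3.2 and Key 1 on whether repeats count.

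The cost is one or two SAP sentences and one derived variable, plus that alignment of the protocol wording. No new data are needed, because GGT is already measured at Screening and Day 1.
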